6.5 Concomitant Therapy

Record in the eCRF all concomitant interventions (e.g., medicines or nondrug interventions) used from the time the participant signs the informed consent until completion of the study, including any changes. For prescription and over-the-counter medicines, vaccines, vitamins, and herbal supplements, record the name, reason for use, dates administered, and dosing information.

Contact the Medical Monitor for any questions on concomitant or prior therapy.

6.5.1 Rescue Medicine

Not applicable.

6.5.2 Permitted Medicines

The only permitted medications are the following:

- Acetaminophen (Paracetamol) up to 1 g per day, at the discretion of the Investigator
- Established treatments for chronic stable concomitant diseases (e.g., for hypertension, hyperlipidemia, etc.) are allowed, when kept stable throughout the study.

Any medicines that are considered necessary to protect the participant's welfare in emergencies may be given at the Investigator's discretion, regardless if it results in a protocol deviation.

Cladribine pretreatment is permitted, provided

- the participant has completed a full first year course of treatment, and
- the second year treatment initiated during this study (Day 8 of Study Period 1) is initiated within 12-18 months after the first dose of cladribine in Year one, and
- lymphocyte count is at least 800 cells/mm³ at Screening and on Day 21 of the Run-in-Period (Baseline) before initiating treatment in year 2.

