4.1 Overall Design

This is a randomized, double-blind, 2-period, 2-sequence crossover study with a 1 month Run-in-Period in pre-menopausal women with active relapsing multiple sclerosis (RMS) requiring a disease-modifying RMS treatment. The overall study design is shown in Section 1.2, Figure 1.

The study design will comprise a ≤ 21 -day Screening period followed by a Microgynon Run-in-Period, followed by 2 sequential treatment periods (Study Periods 1 and 2) of 28 days each.

In case the Screening period lasts > 21 days and ≤ 60 days due to a delayed menstrual cycle of the participant (Run-in Day 1), it is acceptable that the participant starts with a delayed Run-in-Period without having re-performed the Screening assessments (in order to minimize unnecessary investigational burden for the participant). In case of the requirement to re-assess one or more Screening laboratory value(s), the Screening period may be prolonged for up to 8 weeks after the last Screening laboratory assessment and it is acceptable that the participant starts with a delayed Run-in-Period without re-assessing the complete set of Screening laboratory assessments. In both cases, the participant does not need to sign a new Informed Consent Form (ICF).

In the Run-in-Period as well as during both treatment periods, Microgynon (1 tablet/day containing 30 μg ethinyl estradiol [EE] and 150 μg levonorgestrel [LNG]) will be administered for 21 days, followed by 7 days off-treatment. In Study Periods 1 and 2 Microgynon will continue to be administered together with randomized treatment sequences of a 5-day once-daily cladribine 10 mg tablet treatment (Day 9 to Day 13 of Study Period 1) followed by a 5-day once-daily matched placebo treatment (Day 9 to Day 13 of Study Period 2) or vice versa; i.e., participants will be randomized to 1 of 2 double-blind treatment sequences, either cladribine-placebo or placebo-cladribine. Additionally, matched placebo treatment (Day 15 to Day 19) will be given in order to protect the blind for the cladribine-placebo sequence, that will receive their second weekly dose of cladribine on Day 15 to Day 19 in Study Period 2. In turn, the placebo-cladribine sequence will receive the second weekly dose of cladribine after the End of Study Visit as part of standard medical care.

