Participants randomized to the treatment sequence placebo-cladribine, will receive their first 5-day cladribine treatment in Study Period 2 (Days 9 to 13), and will receive their second 5-day cladribine treatment between 28 to 35 days thereafter, which conforms to the approved cladribine posology. It is important to note, that this second cladribine treatment week will not be part of the study itself but provided as standard medical care of participants in the following month after end of the study (see Section 6.7).

Participants randomized to the treatment sequence cladribine-placebo, will receive their first 5-day cladribine treatment in Study Period 1 (Days 9 to 13). Since, according to the study design, they will have to receive Placebo treatment 4 weeks thereafter (i.e., Study Period 2, Days 9 to 13), their second 5-day cladribine treatment will have to be deferred by 6 days (i.e., Study Period 2, Days 15 to 19). Accordingly, participants will receive their second 5-day cladribine treatment 34 days after having received their first cladribine 5-day treatment in Study Period 1. This schedule will only marginally deviate from the approved cladribine posology. In view of the long-lasting duration of action of cladribine, this modest deferral of the second cladribine treatment week is unlikely to affect the overall efficacy of cladribine treatment.

The second cladribine treatment on Days 15 to 19 in Study Period 2 will not alter the primary study objectives, as the treatment is only initiated after all PK and  samples will have been taken on Day 14 with the last sampling in the morning of Day 15 (initiation of second cladribine treatment thereafter).

In order to also enable blinding of the Days 15 to 19 cladribine treatment in Study Period 2, all participants from both treatment sequences will receive placebo on Days 15 to 19 in Study Period 1, and participants randomized to the treatment sequence cladribine-placebo (Days 9 to 13) will receive cladribine on Days 15 to 19 in Study Period 2 as their second dose (see Section 1.2, Figure 1).

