Use of any herbal medications such as St John's Wort, milk thistle/silymarin, goldenseal/berberine and Echinacea, or any dietary supplements (including vitamins and minerals) within 2 weeks prior to the first scheduled study intervention, and expected use such products throughout the study (see Exclusion Criterion #25).

Participants that had undergone a previous 1 year cycle of cladribine may be considered for inclusion into this study as their second year treatment course. Therefore, previous cladribine treatment is permitted, provided the participant has completed a full first year course of treatment and that the second year treatment initiated during this study (Day 9 of Study Period 1 or 2, respectively depending on treatment group) is initiated within 12 to 18 months after the first dose of cladribine in year one. Note that lymphocyte counts for these participants needs to be at least 800 cells/mm³ before initiating cladribine treatment in year 2 (see Section 6.7) rather than within normal ranges (see Inclusion Criterion #4)

The participants are prohibited from using prescription or over-the-counter medications, herbal medicines and dietary supplements (e.g., vitamins and minerals) as detailed in the Exclusion Criteria (see Section 5.2), apart from acetaminophen up to 1 g per day, as judged appropriate by the Investigator, within the specified time-periods prior to the first study intervention during the study, and until after the End of Study Visit.

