90 to < 100	90 mg (9 tablets)	80 mg (8 tablets)
100 to < 110	100 mg (10 tablets)	90 mg (9 tablets)
110 and above	100 mg (10 tablets)	100 mg (10 tablets)

kg=kilogram; mg=milligram

Table 2 above shows how the total number of tablets per treatment week is distributed over the individual days. The daily cladribine doses in each treatment week are to be taken at intervals of 24 hours at approximately the same time each day, i.e., in the morning after an overnight fast. If a daily dose consists of 2 tablets, both tablets are taken together as a single dose. Table 3 below shows the number of tablets to be given for each day as a function of the total numbers of tablets per week.

Table 3 Cladribine 10 mg tablets per week day for study days

Total number of tablets per week	Day 9	Day 10	Day 11	Day 12	Day 13
5	1	1	1	1	1
6	2	1	1	1	1
7	2	2	1	1	1
8	2	2	2	1	1
9	2	2	2	2	1
10	2	2	2	2	2

Days are shown as Study Days as per Schedule of Assessments, where Day 9 of each period is the first day of study intervention administration.

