6.7 Study Intervention after the End of the Study

The dose and the posology of both the examined treatments, cladribine tablets and the monophasic oral contraceptive Microgynon as per this study protocol will be consistent with the labeled use of both products. The study design ensures that participants would be able to receive the full dose and dosage regimen as per label with only minimum deviations, as further described in Section 4.1 and below.

Study participants will be offered the approved 2-year use of cladribine. Following completion of the 2 annual treatment courses, no further cladribine treatment is required in years 3 and 4.

Participants randomized to the treatment sequence cladribine-placebo will receive their first and second 5-day repeat-dose treatments as part of their study participation.

For participants randomized to the treatment sequence placebo-cladribine, only the first cladribine 5-day treatment will be part of the study, while the second cladribine 5-day treatment will be offered to the study participants as medical care in the month after end of study provided by the Sponsor.

Further on, 1 year after having received the first dose of cladribine of the first 5-day repeat-dose treatments (as part of the study), participants will embark into treatment course 2 which also consists of 2 5-day repeat-dose treatments, 1 at the beginning of the first month and 1 at the beginning of the second month of the second treatment year. Cladribine treatment will be provided by the Sponsor outside of the study.

Study participants that enter the study as their second year treatment course (see Section 6.5.3) will complete their full 2-year treatment course during or shortly after the End of Study Visit, and no further treatment will be provided by the Sponsor.

Principal Investigators will be informed of the treatment sequence of each participant once a participant has completed the End of Study Visit, as they need to know whether another dose of cladribine needs to be given. Details on this procedure are described in the IMP Handling Manual.

Criteria for initiating and continuing cladribine therapy are as follows:

Lymphocyte counts must be

- normal before initiating cladribine treatment in Study Period 1 of the study;
- at least 800 cells/mm³ before initiating cladribine treatment in year 2.

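### Protocol 6.5.2 counts the 12–18 month window for second-year participants to Period 1 Day 8, when no cladribine or placebo is given; 6.5.3 counts it to the first cladribine dose, 1 or 29 days later depending on sequence

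*Protocol*

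**What the plan says.** Two current sections of the protocol state one eligibility condition with different dates.

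- Section 6.5.2 (Permitted Medicines) allows cladribine pretreatment provided "the second year treatment initiated during this study (Day 8 of Study Period 1) is initiated within 12-18 months" after the first dose in year one. It makes no distinction by sequence.
- Section 6.5.3 (Prohibited Medicines) repeats the condition but identifies the start as "Day 9 of Study Period 1 or 2, respectively depending on treatment group) is initiated within 12 to 18 months" after that dose.

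The dosing text agrees with 6.5.3. Section 6.6.1 gives cladribine or placebo on Days 9–13 and 15–19, and its note to Table 3 says that "Day 9 of each period is the first day of study intervention administration". Section 4.2 says that women in the placebo-cladribine sequence "will receive their first 5-day cladribine treatment in Study Period 2 (Days 9 to 13").

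Sites do not know the sequence while the woman is in the study: "Principal Investigators will be informed of the treatment sequence of each participant once a participant has completed the End of Study Visit" (section 6.7). The Period 1 Day 8 eligibility re-check in the Schedule of Activities covers contraception, blood loss, lifestyle and laboratory results. It does not mention this window.

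**The concern.** In neither sequence is Period 1 Day 8 the day on which year-two cladribine starts. It is the admission day, and only open-label Microgynon is taken then. In the placebo-cladribine sequence the first cladribine dose comes a full cycle later. A site that follows 6.5.2 literally can therefore accept a woman who is inside 18 months on the date it checks but outside on the date that counts.

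Section 6.5.3 names the right date but in a form that a blinded site cannot apply to an individual, because the date depends on her treatment group. The site would have to work out for itself that both possible dates must fall inside the window.

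At stake is whether second-year women near the upper limit are dosed within the protocol's own time limit. It is a matter of eligibility and posology, not of the PK analysis.

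**Working it through.** **Inputs.** The Run-in-Period is one 28-day cycle (Schedule of Activities) and each study period lasts 28 days (4.1). Cladribine or placebo starts on Day 9 of each period (6.6.1). First cladribine is on Period 1 Day 9 or Period 2 Day 9, according to sequence (4.2).

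**1. Check of the day count against the protocol's own figure.** Absolute day = (period − 1) × 28 + day. From Period 1 Day 9 to Period 2 Day 15 is (28 + 15) − 9 = 34 days. Section 4.2 says the same: "participants will receive their second 5-day cladribine treatment 34 days after having received their first cladribine 5-day treatment in Study Period 1".

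**2. Gap between the 6.5.2 date and the first cladribine dose.**

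| Sequence | First cladribine | Days after Period 1 Day 8 |
|---|---|---|
| Cladribine-placebo | Period 1 Day 9 | 9 − 8 = 1 |
| Placebo-cladribine | Period 2 Day 9 | (28 + 9) − 8 = 29 |

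With an average month of 365.25/12 days, 29 days is 0.95 month. A placebo-cladribine woman at exactly 18 months on Period 1 Day 8 is first dosed at about 18.95 months. At the lower edge the error runs the other way: one at about 11.05 to just under 12 months on Period 1 Day 8 fails 6.5.2 but meets 6.5.3.

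**3. Example under 6.5.2 alone** (dates chosen for illustration). First year-one dose 15 January 2020, so the 18-month date is 15 July 2021. Period 1 Day 8 on 25 June 2021 is 17 months 10 days after that dose and passes. Period 2 Day 9 is 29 days later, 24 July 2021, which is 9 days past the limit.

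**4. Translation to Run-in Day 1.**
- Run-in Day 1 to Period 1 Day 9: 28 + 8 = 36 days.
- Run-in Day 1 to Period 2 Day 9: 36 + 28 = 64 days.

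Both sequences stay inside the window if Run-in Day 1 is no earlier than the 12-month date minus 36 days and no later than the 18-month date minus 64 days. In the example that is 10 December 2020 to 12 May 2021. The woman in step 3 started on 21 May 2021 (25 June minus 35 days), 9 days too late.

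**5. Length of the entry window.** Month 12 to month 18 spans 181–184 days.
- 6.5.2 alone: 181–184 days.
- Both sections met for either sequence (12 months by Period 1 Day 8, 18 months at Period 2 Day 9): 29 days less, 152–155 days.
- Rule in step 4: 28 days less, 153–156 days (153 in the example).

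**The case against.** The strongest reply is that the failure needs a site to read 6.5.2 in isolation. The operative requirement there is that treatment starts within 12–18 months, and Day 8 appears only in a parenthesis. The dosing text puts the first dose on Day 9, section 6.5.3 follows immediately and refers back to 6.5.2, and section 6.5 sends questions on prior therapy to the Medical Monitor. A site that applies both sections and checks Period 2 Day 9 will not dose late. This stands, and it keeps the point small. It does not remove it: the careful site still has to supply a step that the protocol does not state.

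Four stronger readings are tempting and are not supported.

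- *Section 6.7 settles the anchor.* It speaks of "Study participants that enter the study as their second year treatment course (see Section 6.5.3"), but the cross-reference identifies who these women are; it does not rule on timing. The reason to prefer 6.5.3 is that it matches the dosing days.
- *Screening delays enlarge the discrepancy.* Section 4.1 does let the start move ("due to a delayed menstrual cycle of the participant (Run-in Day 1), it is acceptable that the participant starts with a delayed Run-in-Period"), but such a delay shifts the dates under either section. The gap between them remains 1 or 29 days.
- *The lymphocyte-recovery limit in 6.7 is breached.* That limit concerns a year-two course delayed for lymphocyte recovery. A dose that is late through scheduling does not show that recovery took too long.
- *Affected women would be lost from the primary analysis.* SAP 8.1 cites 6.5.2 and 6.5.3 among the sources of important deviations, so a reader might infer this. SAP 8.2 excludes women for deviations that make the data incomparable between treatments, and nothing in the documents suggests that a somewhat late year-two start does so.

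**Conclusion.** Wrong as written, and minor. The two sections give different dates for one eligibility limit. The 6.5.2 date is not a cladribine or placebo dosing day, and the 6.5.3 date cannot be applied to an individual woman by a blinded site. Under 6.5.2 alone, the first year-two dose can fall past 18 months by at most 1 day in the cladribine-placebo sequence and at most 29 days in the placebo-cladribine sequence.

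These figures assume the planned 28-day cycles without slippage. Only second-year women near the edge of the window are affected, and the documents do not give their number. No harm from a start this late is shown. There is no effect on the PK set, power or the primary comparison.

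**What to change.** In both 6.5.2 and 6.5.3, replace only the timing clause with:

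*the planned Day 9 of Study Period 1 is at least 12 months, and the planned Day 9 of Study Period 2 at most 18 months, after the first dose of cladribine in year one.*

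Add the equivalent for sites: Run-in Day 1 no earlier than the 12-month date minus 36 days and no later than the 18-month date minus 64 days, checked before Run-in Day 1. The site needs no knowledge of sequence to apply it.

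Keep the other two conditions unchanged: a completed full first-year course, and lymphocytes of at least 800 cells/mm³. The completed-course condition stands only in these two sections, so replacing the paragraphs whole would delete it.

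The cost is a wording change in two places. The entry window for second-year women becomes 153–156 days. That is 28 days (about 15%: 28/184 to 28/181) shorter than under 6.5.2 read alone, but one day longer than the 152–155 days left when both sections are already applied for either sequence.

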5.1 Inclusion Criteria

Participants are eligible to be included in the study only if all the following criteria apply:

Age

1. Are 18 to 45 Years of age inclusive, at the time of signing the informed consent.

Type of Participant and Disease Characteristics

2. Have a diagnosis of clinically stable and definite RMS by either [McDonald MS](#) or [Poser](#) criteria.
3. Apart from their underlying primary disease condition (i.e., RMS) are in good health as determined by medical history, physical examination, 12-lead ECG, vital signs, clinical biochemistry, hematology and urinalysis.
4. Have white blood cell counts, absolute lymphocyte counts and absolute neutrophil counts within normal ranges (applies for patients in Year 1) at Screening and on Day 21 of the Run-in-Period (Baseline), respectively. Platelets should not be below $100 \times 10^9/L$. In case of second year cladribine treatment, lymphocyte counts must be at least 800 cells/mm³ at Screening and on Day 21 of the Run-in-Period (Baseline).

5. Have other safety laboratory values within normal ranges at Screening, or modestly out of range which are assessed by the Investigator as not clinically relevant.
6. Are able and willing to accept dietary restrictions and restrictions regarding the use of concomitant medications (incl. over-the-counter (OTC)) products, herbal medicines and dietary supplements) over the course of the study as further specified in the Exclusion Criteria.
7. Are able and willing to undergo serial venous blood sampling for pharmacokinetic evaluation.
8. Are able to comply with all of the study requirements.

Weight

9. Have a body weight within ≥ 50 kg and ≤ 100 kg and body mass index (BMI) within the range ≥ 18 kg/m² and ≤ 30 kg/m² (inclusive) at Screening.

Sex

10. Are non-pregnant, non-breast feeding women of any ethnic origin.

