12. Diabetes mellitus (Type 1 or Type 2) with vascular manifestations (e.g., diabetic foot syndrome, retinopathy or arteriosclerosis).
13. Poorly controlled arterial hypertension, i.e., systolic blood pressure ≥ 160 mm, or diastolic blood pressure ≥ 100 mm Hg).
14. Severe hyperlipoproteinemia, i.e., total cholesterol ≥ 240 mg/dL or hypertriglyceridemia ≥ 200 mg/dL in combination with low density lipoprotein (LDL) cholesterol ranging between 160 to 190 mg/dL.
15. Signs and symptoms of Transmissible Spongiform Encephalopathy or Progressive Multifocal Leukoencephalopathy (PML) at Screening.
16. Presence of chronic or recurrent infection or any acute infection within the last 2 weeks before first dosing in treatment periods employing cladribine.
17. Signs or symptoms of neurological disease other than MS that could explain the symptoms of the participant.
18. Presence of gastrointestinal (GI) disease or history of gastrointestinal -tract surgery that, in the opinion of the Investigator, may affect the absorption of the study drugs, i.e., the pharmacokinetic outcome of the study.

Prior/Concomitant Therapy

19. Current immune-suppressive or myelosuppressive therapies (e.g., methotrexate, cyclophosphamide, cyclosporine or azathioprine, or chronic use of corticosteroids) or prior treatment with immunomodulatory or immunosuppressive medicinal products within the last year prior to the planned first study intervention, with the exception of the following therapies and application of the specified wash-out criteria below:
- Interferon b, Dimethylfumarate, and Glatirameracetate (Copaxone): until remission of treatment-specific effects as indicated by a lymphocyte count not below the lower limit of normal range of central lab (1.000 - 1.200 cells/mm³) and at least 1 month,
 - Azathioprine, Cyclosporine A, Mitoxantrone, Methotrexate: until remission of treatment-specific effects as indicated by a lymphocyte count not below the lower limit of normal range of central lab (1.000 - 1.200 cells/mm³) and at least 3 months,
 - Alemtuzumab, Rituximab, until remission of treatment-specific effects as indicated by a lymphocyte count not below the lower limit of normal range of central lab (1.000 - 1.200 cells/mm³) and at least 6 months.

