- Is otherwise considered to be medically important. Important medical events that may not result in death, be life-threatening, or require hospitalization may be considered as SAEs when, based upon appropriate medical judgment, they may jeopardize the participant or may require medical or surgical intervention to prevent 1 of the outcomes listed above. Examples of such events include allergic bronchospasm requiring intensive treatment in an emergency room or at home, blood dyscrasias or convulsions that do not result in inpatient hospitalization, or the development of drug dependency or drug abuse.

For the purposes of reporting, any suspected transmission of an infectious agent via a study intervention is also considered an SAE, as specified below for reporting SAEs, AESIs (Adverse Event of special interest) and DLTs.

Events that Do Not Meet the Definition of an SAE

Elective hospitalizations to administer, or to simplify study intervention or procedures (e.g., an overnight stay to facilitate chemotherapy and related hydration therapy application) are not considered SAEs. However, all events leading to unplanned hospitalizations or unplanned prolongation of an elective hospitalization (i.e., undesirable effects of any administered treatment) must be documented and reported as SAEs.

Events Not to Be Considered as AEs/SAEs

Medical conditions present at the initial study visit that do not worsen in severity or frequency during the study are defined as Baseline Medical Conditions, and are not to be considered AEs.

Adverse Events of Special Interest

Description of selected adverse reactions

Lymphopenia

Only lymphopenia Grade 3 or Grade 4 represents AESIs. In clinical studies, 20% to 25% of the participants treated with a cumulative dose of cladribine 3.5 mg/kg over 2 years as monotherapy developed transient Grade 3 or 4 lymphopenia. Grade 4 lymphopenia was seen in less than 1% of the participants. The largest proportion of participants with grade 3 or 4 lymphopenia was seen 2 months after the first cladribine dose in each year (4.0% and 11.3% of participants with grade 3 lymphopenia in year 1 and year 2, 0% and 0.4% of participants with grade 4 lymphopenia in year 1 and year 2). It is expected that most participants recover to either normal lymphocyte counts or grade 1 lymphopenia within 9 months.

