11.3 Other Baseline Characteristics

Other baseline characteristics will be listed by subject and summarized using the following information from the Screening/Baseline Visit CRF pages.

Other baseline characteristics:

- Smoking status
- Alcohol consumption

12 Previous or Concomitant Medications/Procedures

Previous medications are medications, other than trial medications and pre-medications for trial drug, which started and stopped before first administration of trial drug.

Concomitant treatments are medications, other than trial medications, which are taken by subjects any time on-trial (on or after the first day of trial drug treatment for each subject).

In case the date values will not allow to unequivocally allocating a medication to previous or concomitant medication the medication will be considered as concomitant medication

Any previous and concomitant medication will be encoded with WHO-DD, latest version. Prior and concomitant medications will be listed by subject (all subjects).

The following information will be displayed in a listing: generic or trade name (as reported in CRF), WHO drug name (including coding), dose/unit, route, frequency, reason for use, start/end date and time.

Concomitant procedures will be presented in a data listing.

13 Treatment Compliance and Exposure

A listing of date and time of each drug administration and each blood sampling including time deviations will be provided sorted by subject.

14 Efficacy Analyses

Not applicable.

15 Safety Analyses

The subsections in this section include specifications for summarizing safety endpoints that are common across clinical trials such as adverse events, laboratory tests and vital signs.

Safety data analysis will be conducted on the Safety Analysis Set.

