15.3 Clinical Laboratory Evaluation

The following treatment labels will be used in tables and listings:

- Screening: During the screening period
- Run-in Period: During run-in period

- Microgynon + Placebo or Microgynon + Cladribine: For the measurement on Day 8, Day 9 and Day 14
- Follow-up: During follow-up/end of study period

All laboratory data will be reported with SI units. Laboratory parameters will be listed by subject and time-point and summarized indicating the treatment at the respective time-point using descriptive statistics and Box and Whisker plot for absolute values and change from baseline over time by treatment sequence, period and treatment.

Laboratory values that are outside the normal range will also be flagged in the data listings, along with corresponding normal ranges. Clinically significant abnormalities/outliers as per the Toxicity Grading Scale for Healthy Adult and Adolescent Volunteers Enrolled in Preventive Vaccine Clinical Trials will additionally be listed separately. Clinically significant values will be defined as values with toxicity grading of grade 2 or higher.

'Baseline' refers to the last scheduled measurement before administration of cladribine or placebo on Day 9 of each period. I.e. 'baseline' for period 1 refers to assessments on Day 21 of the run-in period.

Shift tables for post-dose shift (Low, Normal, High, Missing) will also be presented. The shift tables will be presented for follow-up versus screening.

See Appendix 5 of the clinical study protocol for a table of the safety laboratory evaluations.

Safety laboratory values are separated into:

- Hematology
- Biochemistry
- Urinalysis
- Other tests

Descriptive statistics shift tables and box plots will be created only for hematology and biochemistry results.

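### For a second-year woman who enters with lymphocytes below normal, the SAP 15.3 shift table cannot show a further fall; a graded shift from baseline could

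*Protocol*

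**What the plan says.** Entry depends on treatment year. Protocol 5.1, criterion 4, asks first-year women for "absolute lymphocyte counts and absolute neutrophil counts within normal ranges (applies for patients in Year 1", at Screening and on Run-in Day 21. For the others it says: "In case of second year cladribine treatment, lymphocyte counts must be at least 800 cells/mm³ at Screening and on Day 21 of the Run-in-Period (Baseline". Section 6.5.2 repeats the floor ("lymphocyte count is at least 800 cells/mm³ at Screening and on Day 21 of the Run-in-Period (Baseline) before initiating treatment in year 2"), and 6.5.3 makes clear that it replaces the normal-range rule: "rather than within normal ranges (see Inclusion Criterion #4".

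The normal limit appears in exclusion criterion 19, where the wash-out rule requires a "lymphocyte count not below the lower limit of normal range of central lab (1.000 - 1.200 cells/mm³".

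On analysis, SAP 15.3 states: "Shift tables for post-dose shift (Low, Normal, High, Missing) will also be presented". It specifies the comparison as follow-up against screening. The same section plans descriptive statistics and box plots of absolute values and change from baseline by sequence, period and treatment, and a separate listing of values of toxicity grade 2 or higher. SAP 11.3 says "Other baseline characteristics will be listed by subject and summarized using the following information" and names smoking status and alcohol consumption. Treatment year is not there. Protocol 9.4.2 describes the laboratory shifts as post-dose, relative to baseline.

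**The concern.** A three-level shift table works when participants start inside the normal range. First-year women must do so; second-year women need not. A woman who is already Low has no lower category to move to, so the table records no change whatever happens to her count.

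Lymphocytes are the parameter for which this matters most. Grade 3 or 4 lymphopenia is the event that protocol Appendix 4 defines as an AESI, and Appendix 4 quotes a higher Grade 3 rate for the second year ("4.0% and 11.3% of participants with grade 3 lymphopenia in year 1 and year 2"). The shift table is also the only laboratory output in SAP 15.3 that classifies each woman's change into categories. At stake is the readability of one secondary safety display, not the bioequivalence conclusion.

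**Working it through.** The plan gives no figure on this point to reproduce. The check is to classify counts as the table would.

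**Inputs**
- Entry floor, second year: 800 cells/mm³ (protocol 5.1, 6.5.2, 6.5.3).
- Lower limit of normal (LLN): 1,000 to 1,200 cells/mm³ (exclusion criterion 19, reading the point as a thousands separator). Both ends are used.
- Reference value for a large fall: below 500 cells/mm³, the active-monitoring threshold in protocol 6.9.

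**Rule.** Low if count < LLN, Normal if count ≥ LLN. Fall (%) = 100 × (screening − follow-up) / screening.

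| LLN | Screening | Follow-up | Fall | Shift cell |
|---|---|---|---|---|
| 1,000 or 1,200 | 800 | 700 | 100/800 = 12.5% | Low to Low |
| 1,000 or 1,200 | 800 | 499 | 301/800 = 37.6% | Low to Low |
| 1,000 or 1,200 | 800 | 200 | 600/800 = 75.0% | Low to Low |
| 1,000 | 999 | 499 | 500/999 = 50.1% | Low to Low |
| 1,000 | 1,000 | 499 | 501/1,000 = 50.1% | Normal to Low |
| 1,200 | 1,199 | 499 | 700/1,199 = 58.4% | Low to Low |
| 1,200 | 1,200 | 499 | 701/1,200 = 58.4% | Normal to Low |

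Two women with practically the same fall are recorded differently because one started just under the limit. The affected entry band runs from 800 up to the LLN: 1,000 − 800 = 200 or 1,200 − 800 = 400 cells/mm³ wide. Under criterion 4 only second-year women can be in it. A second-year woman at or above the LLN shifts normally.

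**Timing.** Follow-up against screening uses one post-dose value per woman, so the in-period samples that SAP 15.3 labels by treatment (Days 8, 9 and 14) do not enter the table. Protocol 9.4.2 sets baseline as the reference, and SAP 15.3 defines a baseline (for Period 1, Run-in Day 21), but the shift table does not use it. SAP 7 declares no departure from the protocol's methods.

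**Treatment year.** The analysis sets (SAP 8.2), general specifications (9), demographics (11.1), other baseline characteristics (11.3) and laboratory strata (15.3) do not mention it. That the years are pooled is inferred from this silence. A short part of the SAP around 15.6 was not available to check.

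**The case against.** The strongest reply is that the fall is visible elsewhere, and this largely stands. A reader might infer that the plan cannot register lymphopenia in these women. The documents do not support that. SAP 15.1.1 has an overview line for TEAEs of special interest with numbers and percentages of subjects, and 15.2.3.1 lists AESIs. A Grade 3 or 4 case enters both whatever the entry count. Change from baseline, minimum and quartiles, box plots and the grade 2 or higher listing would also show a large fall, and protocol 7.2 requires only 16 evaluable women. The Medical Monitor reviews the counts during the study.

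What remains is narrower. After Run-in Day 21 the white-cell results are withheld from the investigator, who is told of Grade 3 to 4 decreases. Appendix 4 does not treat abnormal laboratory values as AEs unless they bring symptoms, lead to discontinuation or are judged medically important. Falls short of Grade 3 therefore rest mainly on the laboratory displays.

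A reader might also use the 4.0% and 11.3% rates to forecast cases here. Those rates were seen 2 months after the first dose in each year. End of Study falls on Period 2 Day 25 to 28 (Day 21 plus 4 to 7). That is (28 − 9) + 25 = 44 to (28 − 9) + 28 = 47 days after first study cladribine in the cladribine-placebo sequence, and 25 − 9 = 16 to 28 − 9 = 19 days in the other. Neither reaches 2 months, so expected counts from these rates would not describe any table in this trial.

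Two further replies stand. The entry rule in 6.5.2 contains no error; the point belongs to SAP 15.3. Splitting every safety display by treatment year in a Phase I crossover with descriptive safety is largely preference, and a split alone would leave Low to Low as it is.

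**Conclusion.** The point holds as a limited defect of one table. In SAP 15.3, any further fall in a second-year woman who enters between 800 cells/mm³ and the lower limit of normal is Low to Low, and in-period values are omitted although the protocol plans post-dose shifts against baseline. This rests on reading the laboratory limit as 1,000 to 1,200 cells/mm³ and on no year split existing in the unavailable SAP text.

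The practical size cannot be given: the documents do not state how many second-year women are expected, and 6.5.3 says only that they may be considered. If none enters below the limit, the Low-to-Low problem does not arise, though the omission of in-period values remains. The primary PK analysis is unaffected in every case. It is worth changing because the change is small and the parameter is the one behind the trial's AESI.

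**What to change.** In SAP 15.3, for lymphocytes, replace or supplement the Low/Normal/High table with a shift from baseline grade (last scheduled value before the first study cladribine dose) to worst post-dose grade, on the toxicity scale that section already names and including the in-period samples. This would also bring the table into line with protocol 9.4.2.

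State the lymphocyte cut-offs in the SAP and confirm that they match the grading used for the AESI. The documents give neither the cut-offs nor the scale behind Grade 3 and 4, so agreement cannot be checked here. A fall within one grade would still show no shift, which is a reason to keep the change-from-baseline summary beside the table.

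Add cladribine treatment year (first or second) to SAP 11.3, and flag it in the lymphocyte shift table and the AESI listing. A full split of all safety displays is not needed.

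The cost is SAP wording and one re-programmed table. The laboratory data are already collected, and prior cladribine treatment has to be known for eligibility. The downside is small cells for second-year women, so plain counts are enough.
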